11.1 Toxicity monitoring Rule

Bayesian sequential monitoring (1995) will be employed to perform interim safety monitoring targeting a grade 3 and 4 toxicity rate due to the drug of not more than 30% by 3 months. Patients will be monitored in cohorts of 5. Accrual will be stopped early if $\Pr [\text{prob}(\text{toxicity}) > 0.30 \mid \text{data}] > 0.96$. That is, if we determine that there is a greater than 96% chance that the toxicity rate is greater than 30%, then the study will be stopped. We assume a beta (0.6, 1.4) prior distribution for the toxicity rate, which has a mean of 0.3 corresponding to the 30% target toxicity rate. The historical prior is based on a sample of (300, 700). Table 11 depicts stopping criteria. Stopping conditions corresponding to this probability criterion are to terminate accrual if:

Table 10. Toxicity monitoring rules and stopping conditions

If there are this many (or more) patients with ruxolitinib-related, grade 3 or 4 clinically significant toxicity	Stop the study if this many (or fewer) patients
4	5
6	10
9	15
11	20
12	25
14	30
16	35
18	40

This stopping rule was chosen to assure that the probability that this portion of the study will stop early would be approximately 11% if the true rate of toxicity was no more than 30%. The operating characteristics of this rule were generated by the Biostatistics Department's Multic Lean Desktop program (version 1.2.0) and are shown in Table 11.

Table 11. Operating characteristics for toxicity stopping rule

If the true grade toxicity rate is...	Early Stopping Probability	Achieved Sample Size		
		25th, 50th, 75th percentiles		
0.1	0.0006	40	40	40
0.2	0.0127	40	40	40
0.3	0.1073	40	40	40
0.4	0.4311	20	40	40
0.5	0.8225	5	20	30
0.6	0.9808	5	10	15

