Public Description:	
BACKGROUND:
 
Disease-related symptoms impair the quality of life of patients with chronic lymphocytic leukaemia (CLL) who do not require systemic therapy. Available therapies are not specifically aimed at symptom control. Because stimulation of the B-cell receptor activates JAK2 in CLL cells and the JAK2 inhibitor ruxolitinib improves symptoms in patients with myelofibrosis, we postulated that ruxolitinib would improve disease-related symptoms in patients with CLL. We did a phase 2 trial of ruxolitinib to test this hypothesis.
 
METHODS:
 
Symptomatic patients with CLL who did not require systemic therapy were enrolled at MD Anderson Cancer Center (Houston, TX, USA) between Sept 15, 2014, and Sept 20, 2015. Participants were given 10 mg ruxolitinib orally twice a day. Scores on the Brief Fatigue Inventory (BFI), CLL module of the MD Anderson Symptom Inventory (MDASI) and symptom-associated interference in daily activities, were assessed before treatment and after 3 months. This trial is ongoing and is registered at ClinicalTrials.gov (NCT02131584).
 
FINDINGS:
 
41 patients (25 previously untreated for CLL and 16 previously treated) were enrolled. At 3 months, the mean percentage change from baseline in BFI score was 44.3% (SD 35.0, p<0.0001), in symptom interference score was 43.4% (51.5, p<0.0001), and in MDASI score was 42.1% (37.4, p<0.0001). 32 (78%) of the patients experienced 20% or greater reduction in the mean BFI, and 24 (59%) had a reduction of two units or more in worst fatigue score in past 24 hours as assessed by the BFI. The most common grade 3-4 adverse events were neutropenia (n=2 [5%]), hypertension (n=2 [5%]), insomnia (n=1 [2%]), tinnitus and dizziness (n=1 [2%]), and thrombocytopenia (n=1 [2%]).
 
INTERPRETATION:
 
In patients with CLL, ruxolitinib was associated with significant improvements in disease-related symptoms as measured by BFI, MDASI, and symptom interference scores. As of now, 60 patients have been enrolled. Analysis of these patients' outcome is pending.

Protocol Type:	Standard Protocol

Protocol Phase:	Phase II
Version Status:	Activated -- Closed to new patient entry as of 06/07/2019
Version:	11
Document Status:	Saved as "Final"
Submitted by:	[name]--9/13/2018 10:37:04 AM
OPR Action:	Accepted by: [name] -- 9/17/2018 3:40:21 PM

Which Committee will review this protocol?

- The Clinical Research Committee - (CRC)

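### Table 11 understates three achieved-sample-size percentiles by one cohort, and its sample sizes assume no lag between enrolment and the 3-month toxicity reading

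*Combined protocol and SAP*

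**What the plan says.** Section 11.1 describes Bayesian monitoring of drug-related grade 3 and 4 toxicity with a target rate of "not more than 30% by 3 months. Patients will be monitored in cohorts of 5. Accrual will be stopped early if" the posterior probability that the rate exceeds 0.30 is above 0.96. The prior is given as "We assume a beta (0.6, 1.4) prior distribution for the toxicity rate", with a historical distribution based on a sample of (300, 700).

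The consequence of crossing the boundary is put in two ways. One sentence reads "if we determine that there is a greater than 96% chance that the toxicity rate is greater than 30%, then the study will be stopped". The line that introduces Table 10 reads "Stopping conditions corresponding to this probability criterion are to terminate accrual if".

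Table 10 lists toxicity counts of 4, 6, 9, 11, 12, 14, 16 and 18 against 5, 10, 15, 20, 25, 30, 35 and 40 patients. Its column headings qualify the count with 'or more' and the number of patients with 'or fewer'.

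Table 11 gives the early stopping probability and the 25th, 50th and 75th percentiles of "Achieved Sample Size" for true rates of 0.1 to 0.6. Every sample size in it is a multiple of 5.

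Sections 11.0 to 11.2, as supplied, contain no hold on accrual while a cohort completes 3 months, no rule for patients enrolled in the meantime, and no accrual rate. The separate five-patient summary in Section 11.0 comes at 6 to 8 months and holds nothing.

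**The concern.** Table 11 is the protocol's statement of how many patients will be exposed before an unacceptably toxic regimen is halted. Section 11.0 says that standard care for these patients is no treatment, so that exposure matters.

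Two features raised doubt. First, the 25th percentile of 5 at a true rate of 0.5 requires at least a quarter of trials to stop at the first look. That needs 4 or more toxicities in 5 patients, which looks too rare. Second, the endpoint takes 3 months to observe, yet the table moves in clean steps of 5, as if each cohort were read before anyone else entered. If accrual stays open, the number enrolled at stopping differs from the number read.

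**Working it through.** **Inputs.** Boundaries b(n) from Table 10: 4/5, 6/10, 9/15, 11/20, 12/25, 14/30, 16/35, 18/40. Prior Beta(0.6, 1.4), historical Beta(300, 700) and cut-off 0.96 from Section 11.1. The results being checked are those in Table 11.

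**1. Boundaries.** For each n, take the smallest x for which Pr[Beta(0.6 + x, 1.4 + n − x) > Beta(300, 700)] > 0.96. This gives all eight Table 10 counts. (With a fixed 0.30 in place of the historical distribution, the count at n = 20 would be 10 rather than 11, so the table was built on the historical distribution.)

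**2. Stopping probabilities.** Let f(n, x) be the probability of x toxicities in n patients with no earlier stop. Then

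f(n, x) = Σ_j f(n−5, x−j) · C(5, j) p^j (1−p)^(5−j), summed over paths still below b(n−5),

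and the cumulative stopping probability is S(n) = S(n−5) + Σ_{x ≥ b(n)} f(n, x). The first look can be checked by hand at p = 0.5: S(5) = (5 + 1)/32 = 0.1875.

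With looks at 5 to 35, S(35) = 0.0006, 0.0127, 0.1073, 0.4311, 0.8225 and 0.9808 for p = 0.1 to 0.6. These match Table 11 to four decimals, so the design behind the table is identified. Counting the n = 40 row as a stop would give 0.1121 at 0.3 and 0.8575 at 0.5, so Table 11 does not count it as early stopping.

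**3. Percentiles.** The q-th percentile is the smallest n with S(n) ≥ q, or 40 if S(35) < q.

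| Look n | S(n), p = 0.4 | S(n), p = 0.5 | S(n), p = 0.6 |
|---|---|---|---|
| 5 | 0.0870 | 0.1875 | 0.3370 |
| 10 | 0.1929 | 0.4072 | 0.6565 |
| 15 | 0.2111 | 0.4549 | 0.7256 |
| 20 | 0.2447 | 0.5396 | 0.8245 |
| 25 | 0.3451 | 0.7080 | 0.9368 |
| 30 | 0.3936 | 0.7754 | 0.9659 |
| 35 | 0.4311 | 0.8225 | 0.9808 |

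- p = 0.4: 24.47% stop by 20 and 34.51% by 25. The 25th percentile is 25; Table 11 has 20.
- p = 0.5: 18.75% stop at 5 and 40.72% by 10. The 25th percentile is 10; Table 11 has 5.
- p = 0.6: 72.56% stop by 15 and 82.45% by 20. The 75th percentile is 20; Table 11 has 15.

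The other 15 of the 18 entries agree, including all of the rows for 0.1 to 0.3.

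**4. Lag.** This trial's accrual rate is not given, so I assumed 0.5 to 3.4 per month. The top value comes from the symptom trial in the Public Description: 41 patients at the same centre "between Sept 15, 2014, and Sept 20, 2015", which is 370 days, or 41/(370/30.44) ≈ 3.4 per month. Expected entries in 3 months are 3 × rate: 1.5, 3, 6 and 10.2 at 0.5, 1, 2 and 3.4 per month.

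I simulated Poisson accrual to a maximum of 40, under two readings of when the count acts. The second assumes toxicity times uniform over 0 to 3 months. Medians are good to about one patient.

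| Accrual per month | Median enrolled, p = 0.5: cohort must complete 3 months | Median enrolled, p = 0.5: count acts when reached | p = 0.6: cohort must complete | p = 0.6: count acts when reached |
|---|---|---|---|---|
| Table 11 | 20 | 20 | 10 | 10 |
| 0.5 | 21 | 20 | 11 | 10 |
| 1 | 23 | 21 | 13 | 11 |
| 2 | 26 | 23 to 24 | 16 | 13 |
| 3.4 | 30 | 25 | 20 to 21 | 16 |

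At p = 0.5, the chance of halting before all 40 are enrolled is 0.82 without lag. If cohorts must complete 3 months, it falls to about 0.78 at 2 per month and 0.72 at 3.4 per month.

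**The case against.** **The percentiles may follow a program convention.** All 18 entries are matched by taking the look whose cumulative probability is nearest to q (40 if q exceeds the total stopping probability). The 0.4 entry turns on 24.47% against 25%, and no decision rests on any of the three: the rule is justified by roughly 11% early stopping at a 30% rate, which reproduces. This explains the entries but does not make them right, because Table 11 labels them plainly as percentiles. It does limit their weight.

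**Does the rule have to wait for a cohort to mature?** A reader might infer that nothing lets the count act earlier. The documents do not support that. The 'or more' and 'or fewer' headings of Table 10 can be read as stopping once the count is reached. Section 12.0 has adverse events recorded after every protocol visit, and Section 11.2 gives the investigator or a designee responsibility for the rule. On that reading the median overrun at a true rate of 0.5 is only about 0 to 5 patients.

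**Is true exposure necessarily larger than Table 11?** A reader might infer this too, but it is not established. The upper accrual rate comes from a different population, and at 0.5 per month with prompt action the medians equal the table's. Parts of the document were not available, so the absence of a hold or an accrual rate is shown only for the supplied text.

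**Is the n = 40 row never acted on?** That does not follow either. Leaving a crossing at the maximum out of early stopping is conventional, and stopping the study could still have meaning at 40, since Section 4.3 allows treatment for up to 3 years. What stands is that the consequence is not stated.

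**Conclusion.** The point holds in two parts of unequal firmness.

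The percentile errors need no assumption beyond the usual definition of a percentile. Three entries are one cohort (5 patients) too low, all in the favourable direction. The boundaries and the stopping-probability column are correct and should not change.

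The lag is a gap in specification whose size is conditional. Table 11 counts patients read, not patients enrolled. At a true rate of 0.5 the median overrun is about 1 to 10 patients if cohorts must mature, and about 0 to 5 if the count acts when reached. Both ranges rest on the assumed 0.5 to 3.4 per month; the second also rests on uniform toxicity times. The documents do not settle which reading applies.

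The two descriptions of what is stopped, accrual or the study, also need reconciling. None of this shows the stopping rule itself to be wrong.

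**What to change.** 1. In Table 11, change the 25th percentile at 0.4 to 25, the 25th at 0.5 to 10, and the 75th at 0.6 to 20.
2. State in Section 11.1 that the Table 10 count applies as events occur, as its headings suggest, and that patients still inside their 3-month window are not counted as free of toxicity.
3. Recompute the achieved sample size as patients enrolled, under a stated accrual rate and the 3-month window. Otherwise, label the column as assuming no lag.
4. Reconcile the wording on terminating accrual with the wording on stopping the study, and say what the n = 40 row triggers.

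The cost is a few sentences and one re-run of the table, with no extra patients or visits. The stated figures become slightly less favourable.

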11.2 Trial Conduct

The PI or designee will be responsible for assessing the toxicity monitoring and early stopping rules. The biostatistical collaborators will be available for any assistance.

Protocol specific data and adverse events will be entered into PDMS/CORe. PDMS/CORe will be used as the electronic case report form for this protocol.

The Investigator or physician designee is responsible for verifying and providing source documentation for all adverse events and assigning the attribution for each event for all subjects enrolled on the trial.

12.0 REPORTING REQUIREMENTS

Adverse events will be reported in accordance with the Leukemia-specific Adverse Event Recording and Reporting Guidelines (Appendix G). Adverse events will only be collected up to 30 days after the last dose of ruxolitinib. Adverse event reporting will be as per the NCI version 4 criteria and the MDACC Leukemia Specific Adverse Event Recording and Reporting Guidelines.

Adverse events will be recorded on the Adverse Event Record (AER) for each patient after every protocol visit. The Principal Investigator will sign and date the Adverse Event record for every patient after every protocol visit. Following signature, the Adverse Event Record will be used as source documentation for the adverse events for attribution.

Concomitant medications will be captured in the electronic medical record and not needed in the data capture.

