2.2.10 Warnings and precautions

Thrombocytopenia, Anemia and Neutropenia

Treatment with Jakafi can cause thrombocytopenia, anemia and neutropenia.. Manage thrombocytopenia by reducing the dose or temporarily interrupting Jakafi. Platelet transfusions may be necessary

Patients developing anemia may require blood transfusions and/or dose modifications of Jakafi. Severe neutropenia (ANC less than $0.5 \times 10^9/L$) was generally reversible by withholding Jakafi until recovery. Perform a pre-treatment complete blood count (CBC) and monitor CBCs every 2 to 4 weeks until doses are stabilized, and then as clinically indicated.

Risk of Infection

Serious bacterial, mycobacterial, fungal and viral infections have occurred. Delay starting therapy with Jakafi until active serious infections have resolved. Observe patients receiving Jakafi for signs and symptoms of infection and manage promptly.

Tuberculosis

Tuberculosis infection has been reported in patients receiving Jakafi. Observe patients receiving Jakafi for signs and symptoms of active tuberculosis and manage promptly. Prior to initiating Jakafi, patients should be evaluated for tuberculosis risk factors, and those at higher risk should be tested for latent infection. Risk factors include, but are not limited to, prior residence in or travel to countries with a high prevalence of tuberculosis, close contact with a person with active tuberculosis, and a history of active or latent tuberculosis where an adequate course of treatment cannot be confirmed.

For patients with evidence of active or latent tuberculosis, consult a physician with expertise in the treatment of tuberculosis before starting Jakafi. The decision to continue Jakafi during treatment of active tuberculosis should be based on the overall risk-benefit determination.

PML

Progressive multifocal leukoencephalopathy (PML) has occurred with ruxolitinib treatment for myelofibrosis. If PML is suspected, stop Jakafi and evaluate.

Herpes Zoster

Advise patients about early signs and symptoms of herpes zoster and to seek treatment as early as possible if suspected.

Hepatitis B

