8.1 Outside Physician Participation during Treatment

1. MDACC Physician communication with the outside physician is required prior to the patient returning to the local physician. This will be documented in the patient record
2. A letter to the local physician outlining the patient's participation in a clinical trial will request local physician agreement to supervise the patient's care (Appendix H)
3. Protocol required evaluations outside MDACC will be documented by telephone, fax or e-mail. Fax and/or e-mail will be dated and signed by the MDACC physician, indicating that they have reviewed it.
4. Changes in drug dose and/or schedule must be discussed with and approved by the MDACC physician investigator, or their representative prior to initiation, and will be documented in the patient record.

5. A copy of the informed consent, protocol abstract, treatment schema and evaluation during treatment will be provided to the local physician.
6. Documentation to be provided by the local physician will include drug administration records, progress notes, reports of protocol required laboratory and diagnostic studies and documentation of any hospitalizations.
7. The home physician will be requested to report to the MDACC physician investigator all life threatening events within 24 hours of documented occurrence.
8. Patient will have a physical exam every 1-2 months.

Patients are allowed to have hematology and biochemistry tests performed in outside laboratory facilities. Laboratory results will be obtained by the research staff assigned to this study. The PI or treating physician listed on the delegation of authority log will review outside labs and determined the clinical significance of these labs. The physician will sign and date the outside lab result.

Follow-ups and disease burden assessments will only be performed by the MD Anderson Cancer Center team. Patients must be followed for SAE/AEs until at least 30 days after the last dose of study drug. SAE/AE will be assessed on their next visit to the leukemia clinic at MDACC. Participant will be removed from the protocol study after the 30-day post-treatment visit/assessment.

All protocol specific data will be entered into PDMS/CORe.

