8.3 Disease Response Assessment

Assessment of clinical response will be conducted in accordance with our standard of care (physical examination, CBC, a bone marrow aspiration, and a whole body CT scan to be done at screening and 6 ± 2 months into treatment).

The IWCLL response criteria (Hallek et al., 2008) (Table 8) will be used to assess disease response. A bone marrow aspiration, a whole body CT scan is to be done at screening and 6 ± 2 months into treatment to further assess response. If a 20% reduction in tumor burden is observed at 6 ± 2 months, Treatment will be continued.

Table 8. Response definition after treatment for patients with CLL/SLL, using the parameters of Tables 1 and 3

Parameter	CR*	PR*	PD*
Group A			
Lymphadenopathy [‡]	None > 1.5 cm	Decrease \geq 50%	Increase \geq 50%
Hepatomegaly	None	Decrease \geq 50%	Increase \geq 50%
Splenomegaly	None	Decrease \geq 50%	Increase \geq 50%
Blood lymphocytes	< 4000/ μ L	Decrease \geq 50% from baseline	Increase \geq 50% over baseline
Marrow [‡]	Normocellular, < 30% lymphocytes, no B-lymphoid nodules. Hypocellular marrow defines CRi (5.1.6).	50% reduction in marrow infiltrate, or B-lymphoid nodules	
Group B			
Platelet count	> 100 000/ μ L	> 100 000/ μ L or increase \geq 50% over baseline	Decrease of \geq 50% from baseline secondary to CLL/SLL
Hemoglobin	> 11.0 g/dL	> 11 g/dL or increase \geq 50% over baseline	Decrease of > 2 g/dL from baseline secondary to CLL/SLL
Neutrophils [‡]	> 1500/ μ L	> 1500/ μ L or > 50% improvement over baseline	

Group A criteria define the tumor load, group B criteria define the function of the hematopoietic system (or marrow).

[‡]* CR (complete remission): all of the criteria have to be met, and patients have to lack disease-related constitutional symptoms; PR (partial remission): at least two of the criteria of group A plus one of the criteria of group B have to be met; SD is absence of progressive disease (PD) and failure to achieve at least a PR; PD: at least one of the above criteria of group A or group B has to be met.

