12.1 Adverse Events

An adverse event is the appearance or worsening of any undesirable sign, symptom, or medical condition occurring after starting protocol intervention, up to 30 days after the last dose of ruxolitinib, even if the event is not considered to be related to study drug. Medical conditions/diseases present before starting study drug are only considered adverse events if they worsen after starting study drug. Abnormal laboratory values or test results constitute adverse events only if they induce clinical signs or symptoms, are considered clinically significant, or require therapy.

As far as possible, each adverse event should be evaluated to determine:

1. the severity grade (mild, moderate, severe) or (grade 1-4)
2. its relationship to the study drug(s) (suspected/not suspected)
3. its duration (start and end dates or if continuing at final exam)
4. action taken (no action taken; study drug dosage adjusted/temporarily interrupted; study drug permanently discontinued due to this adverse event; concomitant medication taken; non-drug therapy given; hospitalization/prolonged hospitalization)
5. whether it constitutes a serious adverse event (SAE)

Information about common side effects already known about the investigational drug can be found in the [Investigators' Brochure] (Appendix C)..

Adverse events will be reported in accordance with the Leukemia-specific Adverse Event Recording and Reporting Guidelines (Appendix G), and as per the NCI CTCAE criteria version 4.

Only unexpected AEs will be recorded in the Case Report Form (CRF). The PI or designee will be responsible for assigning attribution of adverse events to the study agent.

The Principal Investigator will sign and date the PDMS Case Report Form toxicity pages per each patient approximately every 3 months. Following signature, the Case Report Form will be used as source documentation for the adverse events for attribution.

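### Other treatments that can move the endpoints, chiefly the permitted anti-CD20 antibody and leukapheresis, are left out of the trial database and have no analysis rule

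*Combined protocol and SAP*

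**What the plan says.** Section 12.0: "Concomitant medications will be captured in the electronic medical record and not needed in the data capture". Section 11.2 identifies the database in question: "PDMS/CORe will be used as the electronic case report form for this protocol". Together these place other medications in the hospital chart and outside the analysis dataset.

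Two other routes could bring in part of this information. Section 12.1 lists, among the actions to note for each adverse event, "concomitant medication taken; non-drug therapy given", but the same section adds "Only unexpected AEs will be recorded in the Case Report Form (CRF". Section 8.1 sets out what local physicians send: "Documentation to be provided by the local physician will include drug administration records, progress notes, reports of protocol required laboratory and diagnostic studies", and the list ends with hospitalisations. It names neither other medications nor transfusions.

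Section 10.0, item 3, permits anti-CD20 antibody or leukapheresis if needed while the patient stays on study. Item 2 removes a patient for transfusion-requiring toxicity only if dose adjustment does not relieve it. Section 2.2.10 warns: "Patients developing anemia may require blood transfusions and/or dose modifications of Jakafi". Exclusion criterion 8 bars interacting drugs but lets the investigator override it.

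Section 8.3, Table 8, says that "group B criteria define the function of the hematopoietic system (or marrow". As printed, its Group B thresholds carry no condition on transfusion or growth factor. Section 11.0 counts early drop-outs as non-responders and has no rule for patients who receive other treatment.

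**The concern.** This is a single-arm trial, so whatever happens between baseline and 6 ± 2 months is credited to ruxolitinib. Anti-CD20 antibody can lower both lymphocyte count and tumour burden; leukapheresis lowers the lymphocyte count. Blood lymphocytes are a Group A criterion in Table 8, and change in tumour burden is the variable in the primary paired t-test. Time to next treatment has the same problem: the plan does not say whether the permitted antibody counts as a next treatment, and the dataset would not hold its date.

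The second exposure is the meaning of Group B. A count held up by transfusion or growth factor does not measure marrow function, yet nothing printed in Table 8 stops it from qualifying.

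A third, smaller one is toxicity attribution. Section 11.1 counts ruxolitinib-related grade 3 or 4 events. Section 2.2.4 reports ruxolitinib AUC changes of +91% with ketoconazole, about +100% to +300% with fluconazole (simulated) and -61% with rifampin. The dataset would not show whether such a drug preceded an event.

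**Working it through.** **1. What reaches the dataset.** Anti-CD20 antibody is a medication, so the Section 12.0 sentence keeps it out of PDMS/CORe. Leukapheresis and transfusion are not medications, and no section says where they are recorded. The adverse-event route notes that something was given, without agent or treatment dates. It also covers only unexpected events in the CRF, whereas cytopenias are known effects of the drug (Sections 2.2.9 and 2.2.10). Off-site care is possible: blood counts may be done locally, and after month 8 every other visit may be local (Section 4.4).

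**2. The plan's own figure.** Inputs from Section 11.0: 17 patients at the interim, 34 at the end, stop if the mean change is below zero, otherwise a paired t-test against no change. Two-sided alpha of 0.05 is assumed because none is stated. With 100,000 simulated trials per scenario, all eight rows of Table 9 reproduce to within 0.01. For difference 1 and SD 2, power is 0.807 against 0.8064 printed, and early stopping 0.019 against 0.0202.

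**3. Illustration of misattribution.** Take no ruxolitinib effect and SD 2. Let a share f of patients receive other treatment that lowers the burden score by d units, so the mean shifts by f × d (for example 0.10 × 2 = 0.2). Both f and d are assumptions. Probability of a significant result:

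| f | d = 1 | d = 2 | d = 4 |
|---|---|---|---|
| 0% | 0.024 | 0.025 | 0.026 |
| 5% | 0.035 | 0.045 | 0.066 |
| 10% | 0.046 | 0.076 | 0.146 |
| 20% | 0.079 | 0.177 | 0.413 |

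The value at f = 0 is near 0.025 rather than 0.05 because the futility look stops about half of null trials.

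**4. Response rate.** Enrolment is 34/0.85 = 40. If 8 of 40 respond (assumed), the rate is 20% with exact 95% CI 9.1% to 35.6%. If 2 of those responses followed other treatment and are not credited, it is 6/40 = 15%, CI 5.7% to 29.8%.

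**5. Group B logic.**
- *PR* needs two Group A criteria and one from Group B. Entry haemoglobin is at least 12.0 g/dL (Section 3.1.1), already above the 11 g/dL threshold. Support can create a PR only if haemoglobin (≤ 11 g/dL), platelets (≤ 100,000/µL) and neutrophils (≤ 1500/µL) would all fail together without it, with no relative-improvement alternative met.
- *CR* needs every criterion, so one supported count can complete the set. Entry ANC may be as low as 0.5 × 10⁹/L = 500/µL, below the 1500/µL required. All Group A criteria, marrow included, must still be met.
- *PD* through Group B is a CLL-related haemoglobin fall above 2 g/dL or platelet fall of at least 50%. Transfusion can hide either.
- *The 20% tumour-mass limb and the paired t-test* use no Group B count.

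**The case against.** The strongest reply is that nothing is lost. The quoted sentence itself says the medications are recorded. This is one centre with about 40 charts, disease burden is assessed only there, and local physicians must send progress notes, drug administration records and hospitalisation documents. That stands against a reading that a reader might infer, namely that these treatments cannot be identified: they can be abstracted. It does not supply a handling rule or put the data in front of the analyst, and off-site records may be incomplete.

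Other stronger readings also fail:
- That transfusions are expressly excluded from data capture. The sentence speaks of medications; transfusions are simply not addressed.
- That transfused counts will manufacture partial responses. Step 5 shows this needs three simultaneous failures.
- That the cytopenia rates in Table 2 (for example 30.9% grade 3 anaemia) can be turned into a number of affected responses. They come from myelofibrosis, and a supported patient is not a changed response. The public description of the earlier CLL study lists grade 3-4 neutropenia in 2 and thrombocytopenia in 1 of 41 patients, with no anaemia among the most common events, though at 10 mg twice daily.
- That corticosteroids are a known source of bias. The documents supplied do not mention them.

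Finally, some footnote text to Table 8 may be lost in extraction, and the cited IWCLL guideline was not supplied. Either may contain a condition on supported counts, so the Group B point concerns the table as printed.

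**Conclusion.** The concern holds as one of data capture and attribution. Treatments that can move the endpoints are outside the analysis dataset, may be incomplete off site, and have no rule in Section 11.0. The main exposure is the anti-CD20 antibody and leukapheresis that the protocol permits. The Group B gap is secondary: it bears mainly on CR and on masked progression, rarely on PR, and not on the 20% tumour-mass limb.

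The size cannot be fixed from the documents, which do not say how many patients would receive these treatments or how far the tumour burden score would move; the score's units are not defined either. The probabilities in the table are a range under assumptions, not a forecast. They show that a modest share of treated patients is enough to multiply the false-positive probability. This should be changed; it does not invalidate the design.

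**What to change.** - **Section 12.0:** replace the sentence with a targeted log in PDMS/CORe, with start and stop dates, abstracted from the chart and local records. It should cover anti-CD20 antibody or other anti-leukaemic therapy, leukapheresis, transfusions, growth factors, and strong CYP3A4 inhibitors, inducers or fluconazole.
- **Section 8.1:** add the same items to the local physician's list.
- **Section 11.0:** state that a response reached after anti-CD20 antibody, other anti-leukaemic therapy or leukapheresis is not credited to ruxolitinib, with the patient kept in the denominator. Add a sensitivity analysis of the paired t-test without those patients. It should not replace the main analysis, because removing patients for something that happened after baseline can itself bias the result. State whether these treatments are events for time to next treatment.
- **Table 8:** state that Group B counts qualify for CR or PR only if not supported by transfusion or growth factor within a stated window before assessment.

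The cost is one short CRF page, some abstraction time and possibly a slightly lower response rate. No patient's treatment changes.
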